## 3 Clinical Study Plan

### 3.1 Study Design

This is a prospective, post-market, multi-center, clinical evaluation of the AccuLIF system in patients requiring arthrodesis for degenerative disc disease (DDD) which may also include up to Grade I spondylolisthesis or retrolisthesis at one or two levels between L2 and S1. DDD is defined as back pain of discogenic origin with degeneration of the disc confirmed by history and radiographic studies.

### 3.2 Number of Centers

Up to 10 centers will participate in the trial.

### 3.3 Number of Subjects

Approximately 100 subjects will be enrolled in this study.

CONFIDENTIAL

This material is the property of Stryker Spine. Do not disclose or use except as authorized in writing by Stryker.  
Page 17

### 3.4 Estimated Study Duration

The enrollment period is approximately 9 months. The anticipated duration of this trial is approximately 36 months from the time the first patient is consented to the time the last patient is seen for his or her 24 month follow-up visit.

## 4 Subject Eligibility

### 4.1 Inclusion Criteria

All of the following inclusion criteria must be met.

1. Subject is skeletally mature and between 18 and 70 years of age.
2. Subject has one or more of the following diagnoses:  
DDD and up to Grade I spondylolisthesis or retrolisthesis, requiring decompression and arthrodesis at one or two contiguous levels between L2 and S1 as confirmed by CT, MRI, myelography and/or lateral flexion/extension films.
3. Subject has not previously undergone surgery (other than microdiscectomy / laminectomy) at the same or adjacent level.
4. Subject has received conservative (non-surgical) treatment for back pain for a minimum of 6 months and is unresponsive.
5. Subject understands the conditions of enrollment and is willing to sign and date the Informed Consent.
6. Subject agrees to comply with visit schedule and completing study questionnaires.

### 4.2 Exclusion Criteria

Patients may not be enrolled in the study if any of the following exclusion criteria are present.

1. Subject has significant instability of the spine, e.g. isthmic spondylolisthesis or degenerative spondylolisthesis greater than grade 1.
2. Subject has degenerative disorder that requires TLIF at more than 2 levels between L2 and S1.
3. Subject has previously undergone lumbar spine surgery (other than microdiscectomy / laminectomy) at the same or adjacent level.
4. Subject is younger than 18 years of age, or older than 70 years of age.
5. Subject has a BMI of 40 or greater.
6. Subject has a history of metabolic bone disease as defined by any of the following:
  - a. Subject is currently taking prescription medications that increase bone-mineral density (e.g Fosamax®, Didronel®, Forteo®, Zometa®).
  - b. Subject was previously diagnosed with a metabolic bone disease (e.g. lumbar Paget's disease, osteoporosis or osteomalacia)
  - c. Subject has a history of bone fractures suggesting bone disease.

CONFIDENTIAL

This material is the property of Stryker Spine. Do not disclose or use except as authorized in writing by Stryker.  
Page 18

7. Subject has any other metabolic bone disease to a degree that lumbar spine instrumentation would be contraindicated. Subject is osteoporotic. Subject is taking any of the following medications:
  - a. Chronic oral or IV corticosteroid therapy (this is not intended to exclude inhalation medication for asthma)
  - b. Medications known to potentially interfere with bone/soft tissue healing (e.g. methotrexate).
  - c. Prescription medications that increase bone-mineral density (e.g. Fosamax®, Didronel®, Forteo®, Zometa®).
8. Subject has diabetes mellitus requiring daily insulin management.
9. Subject has any of the following:
  - a. Progressive neuromuscular disease; OR
  - b. Rheumatoid arthritis or other autoimmune disease; OR
  - c. Active malignancy within the last 15 years (unless the malignancy was treated with curative intent and there have been no clinical signs or symptoms for at least 5 years); OR
  - d. Active hepatitis; OR
  - e. AIDS, ARC, or is HIV positive; OR
  - f. Syringomyelia at any spinal level; OR
  - g. Any other condition that would interfere with the subject self –assessment of pain, function or quality of life.
10. Subject has allergy to implant materials (titanium, titanium alloy).
11. Subject has active systemic infection or infection localized to the site of implantation.
12. Subject has primary or metastatic tumors involving the spine.
13. Subject has open wounds or inadequate tissue coverage over the operative site.
14. Subject has a history of significant mental illness or mental incapacity.
15. Subject is pregnant or interested in becoming pregnant in the next 3 years.
16. Subject is currently participating in another investigational study for a similar purpose.
17. Subject belongs to a vulnerable population (e.g., prisoner, severe drug abuser, developmentally disabled) that would compromise ability to provide informed consent or compliance with follow-up requirements.
18. Subject is currently a smoker, and will not cease smoking from the time of clinical trial enrollment up through 3 months post-operatively; nicotine users (cigarettes, patch, gum, etc.) for whom post-operative bone stimulation would be prescribed, or has a recent history of alcohol or other substance abuse within the past 2 years.
19. Subject is receiving workers compensation.

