# 6 Device Description

## 6.1 Study Device

The AccuLIF system was launched by Stryker Spine in 2014. AccuLIF is a comprehensive system of instruments and implants, including spacers comprised of titanium alloy, stainless steel and silicone rubber, with different size and height offerings. The AccuLIF expandable lumbar interbody technology offers surgeon users the ability to insert an interbody device at a smaller starting height, place the device in the desired position within the disc space, and then expand the device to the desired height based on patient anatomy to ensure endplate-to-endplate fit.

The patented expansion mechanism utilizes hydraulic pressure to expand the implant in 1mm increments to fill the disc space. The hydraulic expansion mechanism provides tactile and visual feedback during expansion and the mechanical lock offers confirmation that the implant is locked. The small starting height of the implant is designed to help preserve endplate structural integrity, minimize impaction forces during insertion, help reduce nerve root retraction on insertion and during expansion, and help to reduce the potential for neural injury during insertion of the implant. This procedure is done via a transforaminal lumbar interbody fusion, (TLIF) technique and can be performed as an open, MIS or LIS procedure. In an open or minimally invasive TLIF approach, the interbody space is generally accessed from a posterior approach, and an AccuLIF TL implant is inserted into the disc space after discectomy and endplate preparation.

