# 7 Study Evaluations

## 7.1 Pre-operative Visit

During the preoperative (first) visit, inclusion/exclusion criteria will be assessed. After eligibility has been confirmed by the site and the Sponsor, the subject's demographics and medical history

CONFIDENTIAL

This material is the property of Stryker Spine. Do not disclose or use except as authorized in writing by Stryker.

Page 20

will be recorded, preoperative functional evaluation will be completed; neurological status (reflex, sensory, motor; and subject's current pain medications will be documented; SF-12 (Q of L), VAS (back and leg), and ODI(function) will be collected; and AP/Lateral, Flexion/Extension and long standing lateral radiographs and an MRI/CT (to confirm diagnosis) will be taken.

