# 8 Adverse Events

## 8.1 Reporting of Adverse Events

### 8.1.1 General Physical Examination Findings

At screening for inclusion into the study, any clinically significant abnormality should be recorded as a preexisting condition and reported on the History and Physical CRF. From the time of consent forward, any new clinically significant findings or abnormalities that meet the definition of a protocol defined AE must also be recorded and documented as an AE. AEs which are reportable under this protocol include those that related to the device, the index procedure, the lumbar spine and those that meet the definition of serious.

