- Post-surgical muscle and tissue pain;
- Injury to other parts of the spine, such as pedicles and transverse processes that may result in temporary or permanent pain or other neurologic symptoms;
- A solid fusion may put more stress on the disc above or below the fusion, which may lead to other complications over time, such as: loss of proper spinal curvature, abnormal motion, disc degeneration, and pain;
- Cessation of growth of the fused portion of the spine;
- Regional Pain Syndrome (sympathetic nerve response) resulting in burning pain, or other abnormal sensation usually usually in the upper extremities. These include, but are not limited to: autonomic dysfunction, reflexive sympathetic dystrophy, or Homer's Syndrome.

It is anticipated that the adverse events associated with the AccuLIF implant will be similar to those of other spinal implants. Specifically, the AccuLIF implant may:

- loosen, break, or move (migrate) with respect to the other

CONFIDENTIAL

This material is the property of Stryker Spine. Do not disclose or use except as authorized in writing by Stryker.  
Page 34

bones of the spine;

- fail to expand within the interbody space (becomes a static cage);
- move or dislodge from the spine (partially or completely), causing injury to nearby organs and tissues in the lower back including blood vessels, nerve roots, spinal cord, dural sac
- fracture the endplate portion of the vertebra, subside, or dislodge a bone fragment during implantation or over time
- Surgical instruments used in the procedure may break, resulting in loose fragments of instrument material, (which is not implantable grade) in the body. Removal of these fragments may cause damage to bones and/or soft tissues. Non-removal of these fragments may cause adverse allergic reactions or injury to sensitive nearby organs.
- Cause adverse / allergic reactions to implant materials (titanium, stainless steel, cobalt-chromium-molybdenum and silicone rubber).
- The bank bone (for the interbody spacer) may transmit infection
- not be positioned properly in the spine, and not maintain proper spinal curvature
- fracture or perforation of the bones of the spine or dislodge bone fragments that may result in temporary or permanent pain or other neurologic symptoms, or surgery;
- cause adverse reactions (titanium)
- collapse at any point post-operatively;
- require another surgery to correct the problem;
- require another surgery to correct improper placement of the device;

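### Exclusion 10 names only titanium and titanium alloy as implant materials, although the protocol says the cage also contains stainless steel and silicone rubber

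*Combined protocol and SAP*

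**What the plan says.** Item 10 of section 4.2 (Exclusion Criteria) reads "Subject has allergy to implant materials (titanium, titanium alloy"), and the parenthesis closes there. The synopsis carries the same wording.

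Section 6.1 (Study Device) describes the AccuLIF system as including "spacers comprised of titanium alloy, stainless steel and silicone rubber".

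Section 12.3 (Expected Complications) introduces a list of device-related events with "Specifically, the AccuLIF implant may". One entry in that list is allergic or other adverse "reactions to implant materials (titanium, stainless steel, cobalt-chromium-molybdenum and silicone rubber").

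Several provisions bear on whether an affected subject would be noticed:

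- Section 7.1 starts preoperative data collection "After eligibility has been confirmed by the site and the Sponsor".
- Section 8.1.1 states: "At screening for inclusion into the study, any clinically significant abnormality should be recorded as a preexisting condition".
- Section 12.4 puts the investigator's medical judgment ahead of the protocol.
- Section 12.2 says the device will be used in line with its labeling.
- Section 11.6 makes enrolling a patient who fails the eligibility criteria a reportable deviation.

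**The concern.** The protocol uses the term *implant materials* twice, each time with a parenthetical list, and the lists differ. The shorter one is in the criterion meant to keep allergic patients out. The longer one is in the risk section, where reactions to the missing materials are anticipated.

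A coordinator who turns item 10 into a screening question may ask about titanium and nothing else. A subject with a known stainless steel or silicone allergy could then be enrolled without anyone seeing a breach of the criterion as listed. Another site, reading the general words broadly, would exclude the same subject or report a deviation. With up to 10 centers, both readings could occur in one study.

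**Working it through.** No figure in the plan depends on this point, so the check is a comparison of texts.

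**Step 1. Materials named in each place.**

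| Material | Item 10 (4.2 and synopsis) | 6.1, spacers | 12.3, allergy entry |
|---|---|---|---|
| Titanium | yes | no | yes |
| Titanium alloy | yes | yes | no |
| Stainless steel | no | yes | yes |
| Silicone rubber | no | yes | yes |
| Cobalt-chromium-molybdenum | no | no | yes |

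Taking the words literally, item 10 names 1 of the 3 materials in 6.1 (titanium alloy) and 1 of the 4 in 12.3 (titanium). Two materials, stainless steel and silicone rubber, are in both 6.1 and 12.3 but not in item 10. One, cobalt-chromium-molybdenum, is in 12.3 only.

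**Step 2. Is the list in item 10 open or closed?** The general words before the parenthesis reach any implant material, and a fair reader can take the parenthesis as illustration. Against that, 4.2 usually marks its illustrative lists. It uses *e.g.* 6 times (items 1, 6a, 6b, 7b, 7c and 17) and *etc.* once (item 18), which makes 7 markers. Two examples are "Medications known to potentially interfere with bone/soft tissue healing (e.g. methotrexate") and "nicotine users (cigarettes, patch, gum, etc".). Item 10 has no marker. The other unmarked parentheses in 4.2 (items 3, 7a and 9c) state exceptions or clarifications, not lists of examples.

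This makes a titanium-only reading possible but does not show it is the intended one. The drafting of 4.2 is not uniform. For instance, the clause on other metabolic bone disease is item 6d in the synopsis but opens item 7 in 4.2. The marker count is therefore limited evidence of how sites will read item 10.

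**Step 3. Would the safeguards catch a titanium-only reading?**

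- The eligibility confirmation in 7.1 adds a second reader, but that reader applies the same item 10.
- Section 8.1.1 would bring out an allergy that is recorded, but it does not tell anyone to ask about steel or silicone.
- Section 12.4 helps only once the allergy is known.

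Together they make it unlikely that a patient with a known allergy would receive the cage. They do not supply the missing question.

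**Step 4. Effect on the statistics.** The primary test concerns the change in segmental lordosis, and the sample size rests on an assumed change, a standard deviation, power and dropout. Item 10 enters none of these.

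**The case against.** The strongest reply is that this is a wording blemish with no practical consequence. The operative words already exclude allergy to implant materials, and the materials are stated in the same protocol. The Sponsor confirms eligibility alongside every site, so one party can apply a single reading, and 11.6 tells centers that anticipate a deviation to ask the Sponsor. Section 12.2 ties use to the labeling, which may itself contraindicate sensitivity to any component.

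The 12.3 list is also visibly merged and partly generic. It follows a statement about other spinal implants, has a second entry on adverse reactions that names titanium alone, and repeats the risk of infection from donor or bank bone. Finally, every subject also receives Xia or ES2 pedicle screws, whose materials the documents do not state, so counting spacer materials covers only part of what is implanted.

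Much of this stands, as to weight:

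- The broad reading is fair, and common Sponsor review makes divergent classification between sites less likely.
- The 12.3 list is weak evidence of what the cage is made of, so the firm comparison is with 6.1. That comparison holds without 12.3.
- The labeling is not in the text available for review, so a contraindication there can be neither assumed nor ruled out.
- The pedicle screws are a reason to keep general words in the criterion, not a reason to leave the list short.

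None of it removes the mismatch between item 10 and the protocol's own device description.

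**Conclusion.** The concern holds. A safety criterion lists fewer materials than the protocol says the device contains. Two spacer materials, stainless steel and silicone rubber, are missing from it, and the protocol anticipates allergic reactions to both.

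The consequence is small. It requires a patient with such an allergy, a site that treats the parenthesis as complete, and safeguards that do not bring the allergy to light. The documents give no basis for estimating how many subjects that would be; it is probably very few. The deviation record could also differ between sites for the same subject. The primary analysis and sample size are not affected. The correction is worth making because it is nearly free and concerns patient safety, not because the study's validity is in doubt.

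Cobalt-chromium-molybdenum is a query, not part of the finding. Section 12.3 attributes it to the AccuLIF implant and 6.1 does not, but the entry may be generic text. The conclusion assumes that 6.1 states the cage materials correctly and that no labeling text, unavailable here, already settles the matter for sites.

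**What to change.** In both the synopsis and section 4.2, reword item 10 to: *allergy to any implant material, including titanium, titanium alloy, stainless steel and silicone rubber*. The word *any* keeps the pedicle screws within the criterion, and *including* marks the list as open. Carry the same wording to the screening form if it has an allergy question.

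Check cobalt-chromium-molybdenum against the product labeling. If an implant used in the study contains it, add it to item 10; if not, delete it from 12.3.

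The cost is one phrase in two places, possibly one line on a form, and at most a very small loss of eligible subjects. The primary analysis and sample size need no change.

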## 5 Subject Enrollment

### 5.1 Treatment Assignment

CONFIDENTIAL

This material is the property of Stryker Spine. Do not disclose or use except as authorized in writing by Stryker.  
Page 19

All subjects will be assigned to receive lumbar interbody fusion via a TLIF approach with the AccuLIF TL implant with supplemental fixation via Xia or ES2 pedicle screws and bone graft from autograph and/or allogenic bone graft comprised of cancellous and/or corticocancellous bone chips.

## 5.2 Randomization

This trial will not include randomization; all subjects will receive the same treatment.

# 6 Device Description

## 6.1 Study Device

The AccuLIF system was launched by Stryker Spine in 2014. AccuLIF is a comprehensive system of instruments and implants, including spacers comprised of titanium alloy, stainless steel and silicone rubber, with different size and height offerings. The AccuLIF expandable lumbar interbody technology offers surgeon users the ability to insert an interbody device at a smaller starting height, place the device in the desired position within the disc space, and then expand the device to the desired height based on patient anatomy to ensure endplate-to-endplate fit.

The patented expansion mechanism utilizes hydraulic pressure to expand the implant in 1mm increments to fill the disc space. The hydraulic expansion mechanism provides tactile and visual feedback during expansion and the mechanical lock offers confirmation that the implant is locked. The small starting height of the implant is designed to help preserve endplate structural integrity, minimize impaction forces during insertion, help reduce nerve root retraction on insertion and during expansion, and help to reduce the potential for neural injury during insertion of the implant. This procedure is done via a transforaminal lumbar interbody fusion, (TLIF) technique and can be performed as an open, MIS or LIS procedure. In an open or minimally invasive TLIF approach, the interbody space is generally accessed from a posterior approach, and an AccuLIF TL implant is inserted into the disc space after discectomy and endplate preparation.

## 6.2 Control Device

No control cohort will be enrolled as part of this study.

## 6.3 Ancillary Devices

The AccuLIF system is indicated for use with supplemental fixation. Stryker supplementation fixation in this study will include either Xia or ES2 systems. The AccuLIF TL cage is indicated for use with autogenous bone and/or allogenic bone graft comprised of cancellous and/or corticocancellous chips. See Appendix X for product instructions for use.

# 7 Study Evaluations

## 7.1 Pre-operative Visit

During the preoperative (first) visit, inclusion/exclusion criteria will be assessed. After eligibility has been confirmed by the site and the Sponsor, the subject's demographics and medical history

CONFIDENTIAL

This material is the property of Stryker Spine. Do not disclose or use except as authorized in writing by Stryker.

Page 20

will be recorded, preoperative functional evaluation will be completed; neurological status (reflex, sensory, motor; and subject's current pain medications will be documented; SF-12 (Q of L), VAS (back and leg), and ODI(function) will be collected; and AP/Lateral, Flexion/Extension and long standing lateral radiographs and an MRI/CT (to confirm diagnosis) will be taken.

## **7.2 Peri-operative Visit**

During the peri-operative visit, the patient will undergo lumbar interbody fusion via the transforaminal approach with the AccuLIF Expandable Interbody Fusion Cage with supplemental fixation in the form of pedicle screws. Surgical details will be collected including: estimated blood loss (EBL), operative times including skin-to-skin and anesthesia time, implant and screw sizes, and any intraoperative complications will be collected at time of surgery. The length of hospital stay will be recorded upon discharge. Any adverse events occurring during surgery through discharge will be collected and reported.

## **7.3 6 Week Visit**

During the 6 week visit (42 days after surgery  $\pm$  2 weeks, study days 28 – 56), SF-12, VAS (back and leg), ODI and patient satisfaction will be collected; neurological status (reflex, sensory, motor); subject's current pain medication, work status, and smoking status will be assessed. AP/Lateral radiographs will be taken.

## **7.4 3 Month Visit**

During the 3 month visit (90 days after surgery  $\pm$  2 weeks, study days 76 – 104), SF-12, VAS (back and leg), ODI and patient satisfaction will be collected; neurological status (reflex, sensory, motor); subject's current pain medication, work status, and smoking status will be assessed. AP/Lateral radiographs will be taken.

## **7.5 6 Month Visit**

During the 6 month visit (180 days after surgery  $\pm$  4 weeks, study days 152 – 208), SF-12, VAS (back and leg), ODI and patient satisfaction will be collected; neurological status (reflex, sensory, motor); subject's current pain medication, work status, and smoking status will be assessed. AP/Lateral radiographs will be taken.

